6.8.2 Prohibited medication

Use of the treatments displayed in the below table are not allowed after the start of study treatment

Table 6-3 Prohibited medication

Medication	Prohibition period	Action taken
Dual antiplatelet therapy	30 days after randomization	Discontinue dual antiplatelet therapy

7 Discontinuation of study treatment and participant discontinuation/withdrawal

7.1 Discontinuation of study treatment

Since this is a one time single dose intravenous infusion, a permanent interruption of the infusion will be considered as discontinuation from study treatment.

Discontinuation of study treatment for a participant occurs when study treatment is permanently stopped for any reason (prior to the planned completion of study treatment administration, if any) and can be initiated by either the participant or the Investigator.

The Investigator must discontinue study treatment for a given participant if, he/she believes that continuation would negatively impact the participant's well-being.

Discontinuation from study treatment is required under the following circumstances:

- Participant/guardian decision
- Any situation in which continued study participation might result in a safety risk to the participant

If discontinuation from study treatment occurs, the Investigator should make a reasonable effort to understand the primary reason for the participant's discontinuation from study treatment and record this information.

Participants who discontinue from study treatment agree to return for the end of treatment and follow-up visits indicated in [Section 1.3](#) Schedule of Activities.

If the participant cannot or is unwilling to attend any visit(s), the site staff should maintain regular telephone contact with the participant, or with a person pre-designated by the participant. This telephone contact should preferably be done according to the study visit schedule.

The Investigator must also contact the IRT to register the participant's discontinuation from study treatment.

7.2 Participant discontinuation from the study

Discontinuation from study is defined as when a participant permanently stops any further protocol-required assessments or follow-up, for any reason.

If the participant agrees, a final evaluation at the time of the participant's study discontinuation should be made as detailed in [Section 1.3](#) Schedule of Activities.

7.3 Withdrawal of informed consent and exercise of participants' data privacy rights

Withdrawal of consent/opposition to use of data and/or biological samples occurs in countries where the legal justification to collect and process the data is consent and when a participant:

- Explicitly requests to stop use of their data
and
- No longer wishes to receive study treatment
and
- Does not want any further visits or assessments (including further study-related contacts)

This request should be as per local regulations (e.g., in writing) and recorded in the source documentation.

Withdrawal of consent impacts ability to further contact the participant, collect follow-up data (e.g. to respond to data queries) and potentially other country-specific restrictions. It is therefore very important to ensure accurate recording of withdrawal vs. discontinuation based on the protocol definitions of these terms.

In this situation, the investigator should make a reasonable effort (e.g. telephone, e-mail, letter) to understand the primary reason for the participant's decision to withdraw their

consent/exercise data privacy rights and record this information. The investigator shall clearly document if the participant has withdrawn his/her consent for the use of data in addition to a study discontinuation.

Where consent to the use of Personal and Coded Data is not required in a certain country's legal framework, the participant therefore cannot withdraw consent. However, they still retain the right to object to the further collection or use of their Personal Data.

Study treatment must be discontinued and no further assessments will be conducted, and the data that would have been collected at subsequent visits will be considered missing.

Further attempts to contact the participant are not allowed unless safety findings require communicating or follow-up.

If the participant agrees, a final evaluation at the time of the participant's withdrawal of consent/opposition to use data/biological samples/exercise data privacy rights should be made as detailed in [Section 1.3 Schedule of Activities](#).

Further details on withdrawal of consent or the exercise of participants' data privacy rights are included in the corresponding informed consent form.

7.4 Lost to follow-up

For participants whose status is unclear because they fail to appear for study visits or fail to respond to any site attempts to contact them without stating an intention to discontinue from study or withdraw consent (or exercise other participants' data privacy rights), the investigator must show "due diligence" by documenting in the source documents steps taken to contact the participant, e.g. dates of telephone calls, registered letters, etc. A participant should not be considered as lost to follow-up until due diligence has been completed or until the end of the study.

7.5 Early study termination by the Sponsor

The study can be terminated by Novartis at any time.

Reasons for early termination include (but are not limited to):

- Unexpected, significant, or unacceptable safety risk to participants enrolled in the study
- Decision based on recommendations from applicable board(s) after review of safety and efficacy data
- Discontinuation of study treatment development

In taking the decision to terminate, Novartis will always consider participant welfare and safety. Should early termination be necessary, participants must be seen as soon as possible and treated as a participant who discontinued from the study. The participant should come in for a final End of Study (EOS) visit. The investigator may be informed of additional procedures to be followed in order to ensure that adequate consideration is given to the protection of the participant's interests. The investigator or Novartis depending on local regulation will be responsible for informing Institutional Review Boards (IRB)/Independent Ethics Committees (IEC) of the early termination of the study.

8 Study Assessments and Procedures

Study procedures and their timing are summarized in [Section 1.3](#) Schedule of Activities. Protocol waivers or exemptions are not allowed.

Adherence to the study design requirements, including those specified in [Section 1.3](#) Schedule of Activities, is essential and required for study conduct.

Repeat or unscheduled samples may be taken for safety reasons or for technical issues with the samples.

8.1 Screening

Re-screening is not allowed if a participant fails screening and does not meet eligibility criteria.

8.1.1 Eligibility Screening

Patients admitted to ICU or intermediate/HDU care with AKI and a suspected or proven sepsis can be considered to be enrolled in the study.

The following key assessments and procedures will be performed at the screening visit:

- Signature of the ICF by the participant, or his/her legal representative, or other according to local regulatory requirements.
- Sepsis and AKI diagnosis
- SOFA score
- Hematology (local lab)
- Clinical Chemistry (local lab)
- Hepatitis screen (local lab)
- [REDACTED]
- Collection of demographics, vital signs, medical history/current medical conditions (including alcohol and smoking history), and concomitant medications
- Reference serum creatinine
- Pregnancy test (serum) performed by local laboratory.

8.1.2 Information to be collected on screening failures

Participants who sign an informed consent form and subsequently found to be ineligible prior to randomization will be considered a screen failure. The reason for screen failure should be recorded on the appropriate case report form. The demographic information, informed consent, and Inclusion/Exclusion pages must also be completed for screen failure participants. No other data will be entered into the clinical database for participants who are screen failures, unless the participant experienced a serious adverse event during the screening phase (see SAE [Section 8.6.2](#) for reporting details). If the participant fails to be randomized, the IRT must be notified within 2 days of the screen fail that the participant was not randomized.

Participants who are randomized and fail to start treatment, e.g. participants randomized in error, will be considered an early terminator. The reason for early termination should be recorded on the appropriate case report form.

8.2 Participant demographics/other baseline characteristics

Country-specific regulations should be considered for the collection of demographic and baseline characteristics in alignment with eCRF.

The following key assessments will be performed at the baseline (Day 1) visit, unless otherwise specified:

- Vital signs (temperature, heart rate, respiratory rate, and blood pressure)
- AKI diagnosis
- APACHE II score
- SOFA score
- [REDACTED]
- Clinical chemistry (local lab)
- Hematology (local lab)
- Urinalysis (local lab)
- PK/PD/ADA blood collection (central lab)
- Urine collection (central lab)
- Serum creatinine, creatinine clearance (central lab)

Demographics, relevant medical histories and current medical conditions collected at screening visit are considered as baseline.

8.2.1 Demographics and Medical History

Demographics to be collected include age, sex, race/predominant ethnicity (if permitted) and medical history (until date of signature of informed consent) should be recorded at screening. Medical history at screening should be recorded in the appropriate section of the eCRF with special emphasis on pre-existing renal disease and the use of immunosuppressant medication, steroids, and nephrotoxic drugs.

For determination of study drug dosage and calculation of fluid corrected creatinine, body weight (in kg/lb) should be estimated or measured.

Height and weight will be collected at screening for calculation of body mass index (BMI) (BMI= body weight (kg)/[height (m)]²). Depending on availability, the order of preference for weight value to be used for dose calculation is:

1. Hospital admission measured weight
2. Patient reported weight
3. Ideal body weight (Devine formula)([Devine, 1974](#))
 - Men = 50kg +2.3kg x (height - 60inches)
 - Women = 45.5kg +2.3kg x (height - 60 inches)
4. Estimated body weight

8.3 Efficacy assessments

Planned time points for all efficacy assessments are provided in [Section 1.3 Schedule of Activities](#).

For additional information on PK, refer to [Section 8.7](#).

8.3.1 Creatinine clearance (CrCl)

Creatinine clearance is the volume of blood plasma cleared of creatinine per unit time. It can be measured using the comparative values of creatinine in blood and urine. To calculate the time corrected endogenous creatinine clearance, paired urine and serum creatinine samples will be collected from participants at all visits from baseline to Day 90/EOS and shipped to the central laboratory.

For the 6 hour measurement, one serum creatinine sample will be collected at the midpoint of the 6 ± 1 hour urine collections. When participants are discharged from the hospital, 6-hour urine collection at home is not considered feasible or reliable; thus, it will not be performed. As a result, 24-hour urine collection should be considered once patients have been discharged home. For the 24 hour creatinine clearance calculation, urine collection should take place one day prior to the study visit, and one serum sample will be taken at the approximately 24 hours later at the study visit. Calculations will be performed by the central laboratory. If reliable urine collection is not possible, one serum creatinine sample still needs to be taken for calculating eGFR ([Delgado et al., 2021](#)).

Urine must be collected for a period of 6 ± 1 hour for each study visit day the participant is admitted in hospital. Baseline creatinine clearance should be performed prior to administration of the study treatment. The collection period will take a minimum of 5 hours, and a maximum of 7 hours. The exact duration of urine collection period and of volume collected will be recorded in the eCRF. The volume should be corrected to account for the volume of samples previously taken from the total urine initially collected. Endogenous creatinine clearance will be calculated as follows: clearance = $(\text{urine volume} \times \text{concentration in urine}) / \text{concentration in serum}$. When participants leave the ICU or intermediate/HDU care unit, but are still in the hospital, the 6-hour urine collection will continue. In case the Foley catheter is removed, a participant might urinate spontaneously. All efforts should be made to begin the 6 hour collection starting at any time after voiding and continue to include a voiding at the 6 hour point. A blood sample for serum creatinine will be drawn at approximately the mid-point of the urine collection. The urine volume produced over the last approximately 6 hours will be entered in the eCRF.

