The routine renal function test of serum creatinine has limitations in patients who are not in a steady state, and other measures of renal function including GFR measured by iohexol are less feasible in the acute setting (Carlier et al., 2015). As a result, and consistent with previous trials in this area, creatinine clearance has been selected as the endpoint for measuring renal function. Creatinine clearance is a reasonable approximation of GFR, not affected by diet, and calculated from the routine in-hospital collection of serum and urine creatinine with no special collection conditions or assays required. It has the further benefit of mitigating both the lack of steady state conditions during the early period of AKI and the reduced creatinine production that characterizes very ill hospitalized patients (Prowle et al., 2014). As an endpoint, it has the advantage of being a continuous variable that provides sufficient power for a phase 2 study compared with the more clinically relevant but categorical measures in the MAKE-30 and MAKE-90 endpoints (i.e., death, RRT, 25% reduction in eGFR).

To calculate the creatinine clearance in mL/min, urine will be collected at every visit over a 6±1 hour period (during hospitalization) with serum creatinine measurements at the midpoint of the urine collection period. Although 24-hour urine collection periods are the most accurate way to reliably determine creatinine clearance, a 6-hour collection period is expected to be representative of the full 24 hours for that day (Baumann et al., 1987, Pickering and Endre., 2012) 24-hour urine collections will occur at visits after patient is discharged from the hospital; serum creatinine will be collected at the end of the 24-hour collection at the site visit.

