8.3.4 Renal replacement therapy (RRT)

Initiation of RRT: RRT should be initiated as per local protocol but recommended based on the criteria described by [Bellomo et al \(2012\)](#). Meeting at least one criterion of the below makes the patient eligible for initiation of RRT:

1. Anuria (negligible urine output for 6 hours)
2. Severe oliguria (urine output < 200 mL over 12 hours)
3. Hyperkalemia (potassium concentrations > 6.5 mmol/L)
4. Severe metabolic acidosis ($pH < 7.2$ despite normal or low partial pressure of carbon dioxide in arterial blood)
5. Volume overload
6. Pronounced azotemia (urea concentrations > 30 mmol/L (> 84 mg/dL) or creatinine concentrations > 300 μ mol/L (> 3.4 mg/dL))
7. Clinical complications of uremia (e.g., encephalopathy, pericarditis, neuropathy)

Timing of termination of RRT: RRT should be terminated as per local protocol but is recommended based on criteria as used in the Veterans Affairs/National Institutes of Health (VA/NIH) Acute Renal Failure Trial Network Study ([Palevsky et al., 2008](#)). If diuresis > 30

mL/hour and there are no other indications for RRT, then endogenous creatinine clearance should be calculated using a 6-hour urine collection period. If endogenous creatinine clearance ≥ 20 mL/min, RRT should be discontinued. If endogenous creatinine clearance ≤ 12 mL/min, RRT should be continued. However, although the criteria for starting and stopping mentioned above are strongly preferred within the protocol setting, based on clinical judgment investigators may deviate from these criteria.

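### The printed creatinine clearance formula leaves out the collection time that the protocol's own definition and mL/min unit require

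*Protocol*

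**What the plan says.** Protocol section 8.3.1 opens with a definition: "Creatinine clearance is the volume of blood plasma cleared of creatinine per unit time". It then names the quantity to be derived: "To calculate the time corrected endogenous creatinine clearance, paired urine and serum creatinine samples will be collected". The rule comes later in the section: "Endogenous creatinine clearance will be calculated as follows: clearance" equals urine volume times concentration in urine, over concentration in serum. That is the whole expression, with no time term.

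The length of collection varies by design. For inpatients, "The collection period will take a minimum of 5 hours, and a maximum of 7 hours". After discharge, "24-hour urine collection should be considered once patients have been discharged home". The same section assigns the calculation to the central laboratory. It also requires the exact length of the collection, and the volume, to be entered in the eCRF; that requirement stands in the paragraph on the 6±1 h inpatient collections.

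Two other sections fix the unit. Section 4.2 says "To calculate the creatinine clearance in mL/min, urine will be collected at every visit over a" 6±1 hour period in hospital. Section 8.3.4, on ending renal replacement therapy, says "endogenous creatinine clearance should be calculated using a 6-hour urine collection period" and compares the result with 20 and 12 mL/min.

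**The concern.** A formula that gives mL cannot be the formula for a quantity the protocol defines as a rate and reports in mL/min. If every collection had the same length, the omission would only rescale the results. Here the length ranges from 5 to 7 h in hospital and becomes 24 h after discharge, so the missing divisor differs between visits and between participants.

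Section 4.2 selects creatinine clearance as the measure of renal function, and it is followed from baseline to Day 90. Many participants may therefore change from the short to the 24 h collection. If time were left out, or replaced by a fixed nominal value, that change alone would raise the result, and it would do so at discharge, when recovery is also expected. The protocol says that its efficacy data should inform later phase 2 work.

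**Working it through.** The documents print no numerical clearance value to reproduce. The check is one of units, followed by an illustration.

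**Units.** Printed rule: V × U / S, with V in mL and U and S in the same concentration unit. The concentrations cancel and mL remains. With time t in minutes, V × U / (S × t) is in mL/min.

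**Why duration drives the printed result.** If true clearance C is constant, V × U / S = C × t. The ratio between two collections is then the ratio of their durations, whatever the value of C.

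**Inputs from the protocol.** Durations of 5, 6 and 7 h (300, 360 and 420 min) in hospital and 24 h (1,440 min) after discharge, from section 8.3.1.

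**Assumptions, not from the documents.** Constant true clearance and U/S = 20. For C = 20 mL/min, urine flow is 20 / 20 = 1 mL/min, so V is 300, 360, 420 and 1,440 mL.

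| Collection | Printed rule, V × 20 | Divided by nominal 360 min | Divided by actual minutes |
|---|---|---|---|
| 5 h | 6,000 mL | 16.7 mL/min | 20.0 mL/min |
| 6 h | 7,200 mL | 20.0 mL/min | 20.0 mL/min |
| 7 h | 8,400 mL | 23.3 mL/min | 20.0 mL/min |
| 24 h | 28,800 mL | 80.0 mL/min | 20.0 mL/min |

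**Ratios.** Within the inpatient window: 8,400 / 6,000 = 1.4. For 24 h against inpatient collections: 28,800 / 7,200 = 4.0, with a range from 28,800 / 8,400 = 3.4 to 28,800 / 6,000 = 4.8.

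**Other clearances.** At a true 12 mL/min the nominal 6 h divisor gives 10.0, 12.0, 14.0 and 48.0 for 5, 6, 7 and 24 h. At a true 60 mL/min it gives 50, 60, 70 and 240. Dividing by the actual duration returns 12.0 and 60.0 throughout. The proportional error is the same in each case: 5/6, 1, 7/6 and 4.

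**The case against.** The strongest reply is that the intended calculation is plain from the surrounding text. Section 8.3.1 defines a rate, calls it time corrected and has the inpatient duration recorded; section 4.2 gives the unit. The calculation is done by a central laboratory, and a result in the thousands would hardly pass as a clearance in mL/min. All of this stands. It is why the literal misuse is unlikely, but it does not rule out the quieter error of dividing by a nominal 6 h, which gives plausible inpatient figures.

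The full formula may also exist elsewhere. Protocol sections 8.3.2 and 9.5, SAP sections 2.8 to 2.10 and the footnote to the urine volume row of the assessment schedule are not visible, and the laboratory manual is outside the documents. This stands too: the absence of a formula in those places cannot be held against the plan. It does not change what section 8.3.1 prints.

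Importance is limited as well. Section 8.3.6 confirms that no efficacy assessment serves a primary or secondary endpoint, section 9.2.1 plans no inference, the interim decision in section 9.8 concerns PK, and the sample size in section 9.9 rests on PK precision.

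A reader might infer from the formula that the reported clearances will not be in mL/min, cannot be compared across visits, and will show a false step in recovery at discharge. The documents do not support that. The intended unit is stated and the inpatient values can be put on one scale from the recorded duration.

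**Conclusion.** The formula in section 8.3.1 is wrong as written: followed exactly, it gives a volume where the protocol requires a rate. The size of the discrepancy under literal use is 1.4-fold across 5 to 7 h and about 4-fold (3.4 to 4.8) for 24 h against inpatient collections. These ratios assume constant clearance during and between collections and depend on nothing else. The defect contradicts the protocol's own definition and unit, and should be corrected, but it is not evidence of wrong results to come.

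Two limits remain. The requirement to record the exact duration is shown for inpatient collections; for the 24 h home collection the visible text says only that serum is drawn about 24 hours later. And dividing by time does not make the two methods identical, because serum is drawn at the midpoint of the 6 h collection and at the end of the 24 h collection.

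**What to change.** Replace the expression in Protocol section 8.3.1 with:

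clearance (mL/min) = (urine volume in mL × urine creatinine) / (serum creatinine × actual collection duration in minutes), with both creatinine values in the same unit.

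State that it applies to the 6±1 h and the 24 h collections, that the divisor is the actual and not the nominal duration, and that the exact duration is also recorded for 24 h collections. Put the same formula in the central laboratory specification, and reconcile sections 8.3.1 and 8.3.4 on units.

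The cost is a line or two of protocol text, the matching entry in the laboratory specification and, if the eCRF does not already capture it, one duration field for the 24 h collection. Visits, samples and sample size do not change.

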8.3.3 Kidney disease improving global outcomes (KDIGO) stage

Determination of severe AKI will be grounded in the staging system outlined in the KDIGO Guidelines for acute kidney injury. This classification system stages AKI into three levels based on the extent of sCr elevation in parallel with the degree and duration of oliguria; patients are classified based on the worst finding (either sCr or oliguria). Three stages of AKI are classified in the table below:

Table 8-1 Staging of AKI

Stage	Serum creatinine	Urine output
1	1.5-1.9 times baseline OR ≥ 0.3 mg/dl (≥ 26.5 μ mol/l) increase	<0.5 ml/kg/h for 6-12 hours
2	2.0-2.9 times baseline	<0.5 ml/kg/h for ≥ 12 hours
3	3.0 times baseline OR Increase in serum creatinine to ≥ 4.0 mg/dl (≥ 353.6 μ mol/l) OR Initiation of renal replacement therapy	<0.3 ml/kg/h for ≥ 24 hours OR Anuria for ≥ 12 hours

